3.4. Hypothesis

12. Given prior evidence of preferential uptake of FS in VS and meningiomas due to disrupted blood brain barrier, we hypothesize that use of intravenous FS will allow for visual differentiation of tumor and surrounding structures and nerves using YE560.
13. The optimal dosing for FS has not been established for this application. Pedro et al utilized 0.5-1.0 mg/kg body weight to visualize peripheral nerve sheath tumors with YE560. The authors found saturation of all tissues with 3-4 mg/kg dose within 18 seconds of administration. The blood-brain barrier may play a modulating role. Schebesch et al (2013) used 3-4 mg/kg to visualize malignant gliomas and observed fluorescence after 20-30 minutes. We suspect that the optimal dose will be 3-4 mg/kg, and peak fluorescence will take a similar amount of time. However, we will initially utilize 1.0 mg/kg SF administered at the time of first visualizing the tumor to enable subsequent doses (up to a maximum of 500 mg or 7 mg/kg). This will allow us

to determine the minimum effective dose and observe the time to peak fluorescence. The optimal dosing strategy will be finalized after the first 10 cases.

14. We hypothesize that the surgeons will be satisfied with the use of SF and YE560, as reflected in responses on the Surgeon Survey. Specifically, we hypothesize that greater than 75% of surgeons would choose to use SF and YE560 at least in the majority of future VS, meningioma, HNP, or HNS resections based on responses from the Surgeon Survey. Secondarily, we hypothesize that surgeons will rate the correlation of fluorescence with visual assessment with white light microscopy and electrostimulation to be “good” or “excellent” for over 75% of the cases.
15. Because the yellow fluorescence is primarily comprised of red and green components, we hypothesize that RGB component analysis of intraoperative images will yield significantly higher red and green values in the VS compared to the facial and cochlear nerves. Similar analysis may be conducted between the tumor and surround nerves or structures of interest for meningiomas, HNP, and HNS.

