3.6.9. Secondary Endpoints

The first secondary endpoint is the differential measurement of red, green, and blue levels in VS tissue compared to the facial nerve and cochlear nerve using FS and YE560. ImageJ software will be used to analyze representative images capture from microsurgery. The operating surgeon will delineate regions of interest for the VS, facial nerve, and cochlear nerve. Separate similar analysis will be performed for other tumor types.

The second secondary endpoint will include gross total resection rate, postoperative facial nerve function, and postoperative hearing status. Facial nerve function will be assessed by clinical evaluation at 3 month postoperative visits as well as intraoperative supramaximal stimulation and minimum stimulation levels as routinely performed in surgery.

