3.6.11. Microscope imaging during YE560 fluorescence use

1. Standard methods of anesthesia as appropriate for open craniotomy or otologic surgery will be used.
2. Surgeons will gain access to the lesion of interest through a craniotomy or translabyrinthine approach.

3. At the time of tumor exposure, patients will be given intravenous FS. The timing and dose may vary. Maximum cumulative dose will not exceed 500 mg.

- Initial dosing protocol will be 1 mg/kg intravenous FS.
 - If insufficient fluorescence is obtained or washout occurs, additional doses of 1 mg/kg may be administered
- Based on the experience of the first 3 cases, modifications to the dosing protocol may be made.
 - A higher, single dose may be administered if there is insufficient fluorescence or premature washout. Additional doses may be given during surgery.
 - If saturation of normal tissue with fluorescence occurs, the dose may be decreased or the FS may be administered at an earlier time point (opening of dura, anesthesia induction, etc.) during subsequent cases
- Continued adjustments may be made to the dosing and timing, with a goal of standardizing the dose after 10 cases

4. Once the VS has been surgically exposed and FS has been administered, the YE560 fluorescence module shall be used to visualize fluorescence in the tissue. Images will be captured prior to tumor dissection, after exposure of the intracapsular tumor contents, and after maximum resection. A pair of images—one using the YE560 and one with white light microscopy—will be captured during each event.

5. With the YE560 turned on, images will be captured with the microscope. Video recording from the Pentero 900 and Kinevo 900 microscopes will be captured for the entirety of their use in the case.

6. The time from injection until to the point where the differential fluorescence is greatest will be recorded and documented in the surgeon's survey. Circulating nursing staff will record timestamps in collaboration with instruction from the operating surgeons.

7. The YE560 module will be applied during the aforementioned events and additionally at the discretion of the operating surgeons. Depending upon the number of potential regions identified for imaging and for possible biopsies, the YE560 fluorescence module is expected to add less than 10 minutes to the overall procedure.

8. At any time, the operating surgeon may turn off the YE560 module as dictated by the needs of surgery.

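### The RGB endpoint does not fix which image is measured, does not log its time since the last fluorescein dose, and requires no image at the timed peak

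*Protocol*

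**What the plan says.** Section 3.6.9 defines the first secondary endpoint as the difference in red, green and blue levels between tumor and the facial and cochlear nerves. Its source is stated in one sentence: "ImageJ software will be used to analyze representative images capture from microsurgery". The operating surgeon outlines the regions of interest. Section 3.5 (item 17) limits the analysis to images that show both the tumor and the nerves, and plans inferential statistics on the result. Section 3.4 predicts significantly higher red and green values in the tumor.

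Section 3.6.11, step 4, sets the still-image schedule: "Images will be captured prior to tumor dissection, after exposure of the intracapsular tumor contents, and after maximum resection". Each event yields one pair, one image with the YE560 filter and one under white light. Step 3 sets the default injection time, "At the time of tumor exposure, patients will be given intravenous FS", and adds "The timing and dose may vary". It also allows repeat doses and, in later cases, earlier administration. Step 6 has the time from injection to greatest differential fluorescence recorded in the surgeon's survey.

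On time course, section 3.4 cites one study that "found saturation of all tissues with 3-4 mg/kg dose within 18 seconds of administration" and another that "used 3-4 mg/kg to visualize malignant gliomas and observed fluorescence after 20-30 minutes". It concludes: "We suspect that the optimal dose will be 3-4 mg/kg, and peak fluorescence will take a similar amount of time".

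**The concern.** The endpoint is meant to quantify how well fluorescence separates tumor from nerve. On the protocol's own account that separation changes with time: the survey in Appendix 3 asks whether contrast rose or fell, when it peaked, whether tissue became saturated and when fluorescence stopped being useful. A measurement that depends on time needs a stated time, or at least a recorded one. The protocol gives neither for the image that supplies the RGB value.

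Two things are at stake. First, if the image is picked once its contrast is known, the tumor-nerve difference tends to be overstated. If it happens to be taken before contrast develops, or after tissue has saturated, the difference is understated. Second, without a recorded image time, nobody can later tell which of these happened or describe how the RGB difference varies with time since dose.

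**Working it through.** No arithmetic reproduces or sizes this point. The protocol gives no expected RGB difference, standard deviation, alpha or power for this endpoint, and no interval from injection to any capture. The check sets the passages side by side.

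1. **What anchors the scheduled images?** Section 3.6.11, step 4, names three events, all surgical. Captures tied to minutes since injection: 0 of 3. Captures tied to observed peak contrast: 0 of 3.

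2. **Is the same event at the same post-injection time in every patient?** No. Step 3 lets dose and timing vary, permits repeat doses during surgery and permits a move to an earlier injection. The interval from last dose to, say, the pre-dissection image therefore differs between patients.

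3. **Can that interval be recovered?** Appendix 3 has clock-time fields for the first, second and third doses, first tumor visualization, peak, saturation and loss of fluorescence. It has none for when a still was taken. Time since last dose = (clock time of image) − (clock time of last dose). The protocol collects the second term but does not require the first.

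4. **Does time plausibly matter?** The two time figures in section 3.4, both at 3-4 mg/kg, are 18 seconds and 20-30 minutes. In seconds the latter is 20 × 60 = 1,200 to 30 × 60 = 1,800, and 1,200/18 ≈ 67 while 1,800/18 = 100. The figures describe different things (saturation of all tissues in one study, observed fluorescence in the other) and come from different tumors, so the ratio does not estimate any error in this trial. It shows only that the protocol cannot treat time since injection as unimportant.

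5. **Which image supplies the value?** The tumor-and-nerve condition in section 3.5 narrows the choice, chiefly to the two captures made before maximum resection plus any discretionary ones. Neither section 3.5 nor 3.6.9 says which of these to use, who chooses, or whether the choice is made before contrast is seen.

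6. **Is the peak captured?** Step 6 times it but requires no image. Step 5 records video for the whole of microscope use. However, YE560 need be on only at the three events and otherwise at the surgeon's discretion (step 7), and it may be turned off at any time (step 8). A frame under YE560 at the peak is therefore possible but not assured. Step 12 assigns the edited video to the survey validation and does not mention the RGB analysis.

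**The case against.** The strongest reply is that this is a largely descriptive feasibility study, that the choice of image can be left to an analysis or imaging plan, and that full-case video with recorded dose and peak times may allow a peak frame to be found. Part of this stands. A later plan could still choose among the images that exist. It cannot create a capture that was never made or a time that was never logged. Image files may carry their own time stamp, but section 2.7 mentions only a session number and nothing requires a stamp to be kept or used. The comparison is also inferential, so descriptive status does not fully cover it.

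Four stronger readings are tempting, and the protocol does not support them.

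- A reader might infer that the endpoint can be left with no tumor to measure, because the last image follows maximum resection. Section 3.5 already restricts the analysis to images with tumor and nerve in view. The first two captures precede maximum resection, and section 3.2 says that complete removal is not always achieved. The third image also has an evident use in looking for residual tumor, which the survey asks about.
- A reader might infer that the first image must precede the peak. The 20-30 minute expectation is a hypothesis from malignant gliomas at 3-4 mg/kg, whereas this study starts at 1 mg/kg and cites the 18-second figure beside it. Injection may also be moved earlier. The first image can precede the peak, but nothing shows that it must.
- A reader might infer that RGB comparisons between doses or tumor types would be confounded with time. None is planned: section 3.1 evaluates dose and timing from surgeon surveys, and section 3.6.9 analyzes other tumor types separately.
- A reader might infer that the surgeon's peak image should be the main measurement. That would select on the outcome. It would also not exist for everyone, because survey item 4 asks for a peak time only if contrast changed.

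**Conclusion.** The point holds as a gap in how the first secondary endpoint is fixed. The protocol does not name the image that supplies the RGB value, does not require that image's time to be logged, and does not require an image at the peak it has timed. Because the image can be chosen after its contrast is seen, and because time since dose varies, the tumor-nerve comparison can be biased upward or downward. The size cannot be computed from the protocol. The conclusion assumes only that contrast changes with time since injection, as the survey questions themselves anticipate. The primary endpoint, a survey response, is not affected.

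**What to change.** - **Section 3.6.9:** replace the reference to representative images with a rule set in advance and applied to every patient. An example is the first scheduled capture before maximum resection in which both the tumor and the nerve being compared are visible. Report the number of patients with no qualifying image.
- **Section 3.6.11, step 4:** log the clock time of each image pair, so that time since the last dose can be derived from the dose times already on the survey.
- **Section 3.6.11, steps 4 and 6:** add one YE560 and white-light pair when the surgeon declares greatest contrast, where a peak is declared. Report it beside the fixed-event image as a supplementary measure labelled maximum contrast, not as the main measurement.
- **Post-resection image:** use it only descriptively, for residual tumor.

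The cost is protocol wording, one extra capture and a timestamp field per case. A fixed-event image may show less contrast than a chosen one. The example rule can also draw on different surgical events in different patients when the nerve is not yet in view, and the logged times let that be described. No change to dose or injection timing is implied.

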3.1. Objectives

Primary objective of this initial feasibility study is to evaluate the benefit of using YE560 to visualize fluorescein sodium (FS) during surgery of VS, Meningioma, HNP, or HNS, determined from surgeon assessment.

Secondary objectives are:

- To evaluate the optimum FS dose and timing to be used with the YE560 device as determined by reported performance on surgeon surveys
- Quantify tissue differentiation of fluorescent VS and adjacent nerves using RGB image analysis
- To report clinical outcomes, including GTR rates, postoperative hearing outcomes, and postoperative facial nerve function

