3.5. Design and Proposed Analysis

16. The feasibility study will involve 90 patients, focusing on intra-operative visualization of fluorescein using YE560 in VS, meningioma, HNP, or HNS, inclusive of recurrent tumors, previously radiated tumors, and patients with neurofibromatosis type 2. There will be an allowance to enroll up to 95 patients to meet the goal of 90 subjects if subjects are withdrawn from the study due to a different pathologic entity diagnosed on biopsy of the tumor. Establishing the optimal dose and timing for FS will be a part of the feasibility study. Flexibility will be allowed with the dose and timing to achieve optimal visualization condition based on surgeon feedback with a maximum cumulative dose of 500 mg (standard dosage for ophthalmology angiography). The study will be largely descriptive, documenting the macroscopic appearance of FS and describing surgeon observations with regards to timing of peak fluorescence, correlation with electrostimulation, and utility in differentiating normal tissue from tumor.
17. Images containing the tumor and facial and cochlear nerves (or other relevant structures of interest in the case of meningioma, HNP, or HNS) will be captured with the microscope with the YE560 filter by the surgeon and analyzed; the YE560 filter will then be turned off and another identical image will be captured under white light microscopy for the separate survey validation analysis. For the RGB component image analysis, the fluorescence of the tumor will be measured in comparison to the facial nerve and cochlear nerve using ImageJ image analysis software to quantify the red, green, and blue components of the images. Inferential statistics will be used to compare the red, green, and blue components of regions of interest from the VS and the adjacent facial or cochlear nerve.
18. For the survey validation analysis, we will validate the question “How well did fluorescence correlate with your visual assessment of the tumor and nerve tissue under normal microscopy without the Yellow 560 filter?” The neurosurgeons and neurologists will be presented with 30-60 second videos of the VS and facial and/or cochlear nerves, with and without YE560 active. The surgeons will respond to the above question with choices of “no correlation,” “some

correlation,” “good correlation,” and “excellent correlation.” Other questions from the surgeon survey will not be validated due to the scope of the feasibility study.

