1. Fluorescein Sodium Administered: _____ ; corresponding event (e.g. opening dura): _____
 - a. If second dose given, time administered: _____, dose _____ mg/kg
 - b. If third dose given, time administered: _____, dose _____ mg/kg
2. Tumor first visualized: _____
3. Did the contrast between the tumor and normal tissue **change after initial visualization of the tumor?**
No change in Contrast over Time / Increased Contrast over Time / Decreased Contrast over Time
4. If there was a change in contrast over time, **when did peak fluorescence** occur such that there was maximum contrast between the tumor and normal tissue? _____
5. Did the tissue become **saturated** with fluorescein such that there was no difference in the fluorescence of nerve and tumor? Yes / No
 - a. If so, when did saturation occur? _____
6. When did the fluorescence diminish such that it was no longer useful _____ / Not Applicable

For the following questions, please circle one number in the boxes below.

7. How well did fluorescence **correlate with your visual assessment** of the tumor and nerve tissue under normal microscopy without the Yellow 560 filter?

No correlation 1	Some correlation 2	Good correlation 3	Excellent correlation 4
---------------------	-----------------------	-----------------------	----------------------------

8. How well did fluorescence **correlate with electrostimulation** (e.g. tissues with high fluorescence do not stimulate, whereas nerve tissues with low fluorescence do stimulate)?

No correlation 1	Some correlation 2	Good correlation 3	Excellent correlation 4
---------------------	-----------------------	-----------------------	----------------------------

9. How helpful was the use of FS and Yellow 560 filter in.... (circle a rating for each row)

	Not helpful at all	Minimally helpful	Somewhat helpful	Very helpful	N/A
Distinguishing tumor from normal nerve	1	2	3	4	0
Preserving facial nerve function	1	2	3	4	0
Preserving hearing	1	2	3	4	0
Detecting residual tumor	1	2	3	4	0

10. Based on the use and performance of FS in this case alone, **how likely are you to use FS** in future cases involving this tumor type (excluding the research trial)?

Unsure 0	Plan to not use in any cases 1	Plan to use in select cases 2	Plan to use in the majority of cases 3	Plan to use in all cases 4
-------------	--------------------------------------	-------------------------------------	--	-------------------------------

Comments for the research team: _____

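### When fluorescein is injected before the tumour is visible, the survey cannot record an earlier contrast peak, so time to peak is left-censored at first view and can reflect surgical access time

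*Protocol*

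**What the plan says.** Timing is a stated purpose (protocol, section 1.3) and part of the first-listed secondary objective in section 3.1: "To evaluate the optimum FS dose and timing to be used with the YE560 device as determined by reported performance on surgeon surveys". Section 3.5 lists, among the descriptive outputs, "describing surgeon observations with regards to timing of peak fluorescence".

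The measurement is set in section 3.6.11, step 6: "The time from injection until to the point where the differential fluorescence is greatest will be recorded and documented" in the surgeon's survey.

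The default injection time is in step 3 of the same section: "At the time of tumor exposure, patients will be given intravenous FS. The timing and dose may vary". If normal tissue saturates, one of two permitted adjustments is that "the FS may be administered at an earlier time point (opening of dura, anesthesia induction, etc.) during subsequent cases". The other is a lower dose. Repeat doses are also allowed: "If insufficient fluorescence is obtained or washout occurs, additional doses of 1 mg/kg may be administered".

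The survey in Appendix 3 records clock times for the first, second and third dose and the surgical event at the first dose (item 1), and the time the tumour was first seen (item 2). Item 3 asks whether contrast was unchanged, rose or fell after that first view. Item 4 opens with "If there was a change in contrast over time" and then has room for one peak time.

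**The concern.** Step 6 counts from injection, but the survey starts watching contrast at first view. When the two coincide, as in the default, the form captures what step 6 asks for. When injection comes first, any peak reached in between is unseen, and the form has no answer that says so. The surgeon can report a fall, which makes first view the best available peak time, or no change, which leaves item 4 blank.

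In the first situation a number is recorded that looks like a time to peak but is the time needed to reach the tumour. In the second, contrast already at its plateau cannot be told apart from contrast that was never useful. An analysis rule can flag the affected cases afterwards, but it cannot recover a peak that nobody observed or an answer that the form did not offer. The affected cases are also not a random subset, because early injection follows saturation in preceding cases.

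**Working it through.** The protocol states no figure for this quantity, so there is none to reproduce. The check traces the form and then sizes the effect.

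**Tracing the form.** Let T be the true time from injection to peak contrast and A the time from injection to first view.

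- Step 6 interval = item 4 time - item 1 time.
- Access time A = item 2 time - item 1 time.
- If contrast falls from first view, item 4 = item 2, so the step 6 interval = A.

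| Case | Item 3 | Item 4 | What is known about T |
|---|---|---|---|
| Injected at exposure (A about 0), contrast later peaks | rose | peak time | T observed |
| Injected early, peak after first view (T > A) | rose | peak time | T observed |
| Injected early, peak before first view, then falling | fell | first-view time | only T ≤ A; recorded as A |
| Injected early, contrast flat after first view | unchanged | blank | at most T ≤ A, if contrast was present at all |

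Where a time is entered, the recorded interval is max(T, A), and the overstatement is max(0, A - T).

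**Sizing.** Inputs:

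- T: 20-30 minutes. Section 3.4 cites this for a glioma study and expects a similar time here. Taken as uniform, mean 25.
- A: not in the protocol. Assumed normal, with the means below and a coefficient of variation of 25%.
- Every early-injected case is taken to have a time entered. Flat cases would be blank instead.

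| Assumed mean access time (min) | Mean recorded interval (min) | Excess over 25.0 (min) | Peaks at or before first view |
|---|---|---|---|
| 0 (injected at exposure) | 25.0 | 0 | 0% |
| 10 | 25.0 | 0 | 0% |
| 20 | 25.6 | 0.6 | 19% |
| 30 | 31.3 | 6.3 | 73% |
| 60 | 60.1 | 35.1 | 99% |
| 120 | 120.0 | 95.0 | >99% |

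With A fixed at 60 minutes, the overstatement in a single case runs from 60 - 30 = 30 to 60 - 20 = 40 minutes.

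**If all cases were pooled**, with an assumed 25% injected early:

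- A = 60: 0.75 × 25 + 0.25 × 60 = 33.75 minutes.
- A = 120: 0.75 × 25 + 0.25 × 120 = 48.75 minutes.

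**Repeat doses.** This is a separate and smaller matter. If the peak comes 25 minutes after the second dose, the interval is 25 minutes from that dose and 25 + g from the first, where g is the gap between doses. For gaps of 10, 20, 30 and 60 minutes that gives 35, 45, 55 and 85 minutes. Both intervals can be calculated from the survey. Step 6 does not say which is meant.

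**The case against.** Several objections carry weight.

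- **Early injection is conditional.** It is offered only in later cases, only after saturation, and as one of two options. Section 3.4 plans the initial dose at first visualization of the tumour, partly so that time to peak can be observed. Those cases are unbiased. This stands and limits the point to the early-injected subset.
- **The affected cases can be identified.** Items 1 and 2 give both clock times, and no section says that early-injected cases will be pooled with the rest. An SAP could separate or censor them. This stands for the analysis. It does not supply the missing answer in item 4.
- **The 20-30 minutes may not apply.** The figure concerns visible fluorescence in gliomas, whereas step 6 concerns the difference between tissues. After saturation, best contrast may come later than 30 minutes, and a longer T shrinks the overstatement. This stands, so the sizes above are illustrative.
- **Time to peak is not a listed secondary endpoint in section 3.6.9.** The objective in section 3.1 is judged on reported performance, and other survey items can be compared across injection events without it. This stands and lowers the stakes, though the quantity remains a named descriptive output.

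A reader might infer that time to peak cannot be derived whenever doses are repeated. The documents do not support that. Times for up to three doses and for the peak are recorded, so the intervals can be calculated. Only the reference dose is unnamed, an SAP could set it, and redosing after exposure adds between-dose time, not access time.

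**Conclusion.** The point holds for cases injected before the tumour is visible. In them, time to peak is left-censored at first view. The survey can return only the first-view time or a blank unless contrast rises afterwards, and the step 6 interval can then be surgical access time. Cases injected at exposure are unaffected.

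The size depends on an access time that the protocol does not give. If the true peak is at 20-30 minutes, the distortion is negligible when access is well under that. At an assumed 60 minutes or more, the recorded value is roughly the access time. How many cases are affected is also unknown.

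It would go too far to conclude that the timing objective fails, or that the reported time to peak will be wrong overall. The default injection time supports a valid measurement, and pooling is not stated. The defect is in a form, bears on a secondary descriptive result, and is best corrected before data are collected, since an unobserved peak cannot be restored later.

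**What to change.** 1. **Appendix 3, item 4.** Have it answered in every case, with four separate choices: an observed peak time; already maximal at first view, then fell; contrast present and unchanged; no useful contrast seen. The last two must stay apart, because only the former implies that a peak level had been reached.
2. **Reporting.** Use items 1 and 2 to identify cases injected before visualization and report them separately. Where contrast was present and then fell or stayed unchanged, report the peak as at or before first view (left-censored), with the access time as the upper bound. Summarise exact time to peak only from cases with a peak observed after first view. Show the number censored beside it, since exact times among early-injected cases come only from the later peaks.
3. **Section 3.6.11, step 6 (minor).** State which injection the interval is counted from when doses are repeated, or report it from both the first and the most recent dose.

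The cost is a revised set of answers to one survey item and a sentence in step 6. The clock times needed are already collected for up to three doses. The drawback is that fewer cases contribute an exact time to peak. The change concerns recording and reporting only and implies nothing about which dose or injection time is right.
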